### **13.1. Treatment of Missing and Spurious Data**

See general definitions in chapter 5.4.

### **13.2. Exclusion of Particular Information**

See general definitions in chapter 5.5.

No data are excluded from the specified analysis set and variables.

### **13.3. Descriptive Analyses**

For specification "Notes = descriptive", see general definitions in chapter 5.1.

### **13.4. Hypotheses & Statistical Tests**

There are no pre-defined statistical hypotheses.

## 14. General Assessments – PHD & Follow-up

### CIP chapter 7.5 Further data of interest

During implantation and follow-ups additional data on safety, performance and usability of the Renamic Neo system and accessories will be collected.

- Use and assessment of PSA functionality (sensing, pacing and impedance tests)
- Success of adequate programming of the implant
- Evaluation of interrogation of the implant including RF telemetry
- Overall assessment of device hardware or software performance including battery use
- Data export evaluation (used connectivity, destination, printing)

...

### 14.1. Analysis Set and Data Selection

All analyses are performed for patients in the PHD and follow-up analysis set using a specific data selection after implantation.

All analyses from chapter 13 Devices and Accessories - Implantation are repeated for these data. However, "implantation" will be replaced by "PHD & follow-up".

---

 analysis set PHD FUP SAR = Yes  
Data selection for general assessments with autom SVTYP ≠ implantation

## 15. Devices and Accessories - Implantation

### CIP chapter 7.5 Further data of interest

#### General information

- Implant type and model, all other implanted devices
- Lead model and programmer software version

During implantation and follow-ups additional data on safety, performance and usability of the Renamic Neo system and accessories will be collected.

... Information on additionally used accessories or other implanted cardiac devices

### 15.1. Analysis Set and Data Selection

All analyses are performed for patients in the implantation analysis set using a specific data selection before / at implantation.

#### Implanted Devices

Data file, identifier patient display id full & DIDVTYP	Notes	Variable name	Variable label	Variable level	Nominal values
device log details	No report	DIDVTYP	General type of device/lead	nominal	
 
○ Pacemaker (single/dual chamber)
 
○ ICD (single/dual chamber)
 
○ CRT-P device
 
○ CRT-D device
 
○ ICM (Insertable Cardiac Monitor)
 
○ RA lead
 
○ RV lead
 
○ LV lead
 
○ VCS lead
 

		DTDVSTAT	Status of device	nominal	
 
○ Implanted and active
 
○ Deactivated but still implanted
 
○ Explanted and returned to manufacturer
 
○ Explanted and discarded
 
○ Attempted implantation, then returned ...
 
○ Attempted implantation, then discarded
 

		DIDVMDL	Device / lead model	text	...

Data file, identifier patient display id full	Notes	Variable name	Variable label	Variable level	Nominal values
data SAR	descriptive	device model SAR 	Device model	text	...

 analysis set imp SAR = Yes  
 Data selection for accessory log details with SVTYP = implantation

 Patient-specific data for  
 [ DIDVTYP = Pacemaker (single/dual chamber) AND  
 DIDVTYP = ICD (single/dual chamber) OR  
 DIDVTYP = CRT-P device OR  
 DIDVTYP = CRT-D device OR  
 DIDVTYP = ICM (Insertable Cardiac Monitor) ]  
 device model SAR = DIDVMDL

Data file, identifier	Notes	Variable name	Variable label	Variable level	Nominal values
patient display id full					
data SAR	descriptive	lead RA model SAR 	RA lead model	text	...
		lead RV model SAR 	RV lead model	text	...
		lead LV model SAR 	LV lead model	text	...
		lead VCS model SAR 	VCS lead model	text	...

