7.5 Further data of interest

General information

- Patient demographics and medical history
- Implant type and model, all other implanted devices
- Lead model and programmer software version

During implantation and follow-ups additional data on safety, performance and usability of the Renamic Neo system and accessories will be collected.

- Use and assessment of PSA functionality (sensing, pacing and impedance tests)
- Success of adequate programming of the implant

- Evaluation of interrogation of the implant including RF telemetry
- Overall assessment of device hardware or software performance including battery use
- Data export evaluation (used connectivity, destination, printing)
- Export of programmer data export files that document the performed use case for evaluation at the sponsor
- Information on additionally used accessories or other implanted cardiac devices

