 IF analysis set enr SAR = Yes AND  
 any general assessments per patient with  
 ([PRSVPRG = Yes AND autom SVTYP = Pre-hospital discharge follow-up (PHD)] OR  
 [PRSVPRG = Yes AND autom SVTYP = Regular follow-up after PHD])  
 THEN analysis set FUP SAR = Yes  
 ELSE analysis set FUP SAR = No

Subgroups

Data file, identifier patient display id full & DIDVTYP	Variable name	Variable label	Variable level	Nominal values
device log details	helpvar device type	hidden technical field: Short name for General type of device	nominal	
 
○ CRT
 
○ CRT-P
 
○ ICD
 
○ ICM
 
○ IPG
 

Data file, identifier patient display id full	Variable name	Variable label	Variable level	Nominal values
data SAR	subgroup device type SAR 	Subgroup type of device	nominal	
 
○ CRT
 
○ CRT-P
 
○ ICD
 
○ ICM
 
○ IPG
 

 Patient-specific type of device data for helpvar device type not missing  
subgroup device type SAR = helpvar device type

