**Renamic Neo and software**

Data file, identifier	Notes	Variable name	Variable label	Variable level	Nominal values
patient display id full & autom SVTYP					
accessory log details	No report	SVTYP	Visit type	nominal	o Implantation o Pre-hospital discharge o Follow-up

Data file, identifier	Notes	Variable name	Variable label	Variable level	Nominal values
patient display id full & SVTYP & helpvar model & DIPRGSNR					
accessory log details (see Analysis Set and Data Selection)	Selection DIPRGM DL = Renamic Neo; no report	DIPRGSNR	Programmer serial number	text	...
		DISFTVER	Programmer software version	nominal	NEO 2004.A ...

Note: In case of any reported problem, the serial number DIPRGSNR of the Renamic Neo, which was used for the specific investigation for a specific patient (or programmers in case more than one programmer were used), will be reported together with the patient id patient display id full.

Data file, identifier	Notes	Variable name	Variable label	Variable level	Nominal values
DIPRGSNR					
renamicneo SAR	descriptive	n imp per renamicneo SAR 	Number of implantations performed with specific Renamic Neo programmer	metric to be reported as nominal	1 2 ...

Data file, identifier	Notes	Variable name	Variable label	Variable Level	Nominal values
patient display id full					
data SAR	descriptive	n renamicneo imp SAR 	Number of Renamic Neo programmers used during implantation	metric to be reported as nominal	1 2 ...
		n renamicneo imp NEO2004A SAR 	Number of Renamic Neo programmers with software NEO 2004.A used during implantation	metric to be reported as nominal	1 2 ...

 Patient-specific data for lead RA model SAR = DIDVTYP = RA lead AND DTDVSTAT = Implanted and active DIDVMDL

 Patient-specific data for lead RV model SAR = DIDVTYP = RV lead AND DTDVSTAT = Implanted and active DIDVMDL

 Patient-specific data for lead LV model SAR = DIDVTYP = LV lead AND DTDVSTAT = Implanted and active DIDVMDL

 Patient-specific data for lead VCS model SAR = DIDVTYP = VCS lead AND DTDVSTAT = Implanted and active DIDVMDL

 Count different patient display id full per DIPRGSNR from accessory log details with SVTYP = Implantation

 Count different DIPRGSNR per patient display id full for SVTYP = Implantation

 Count different DIPRGSNR with DISFTVER = "NEO 2004.A" per patient display id full for SVTYP = Implantation

ECG cable

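### The generator model and the device-type subgroup lack the active-status condition applied to leads, so a non-active generator can be recorded as the patient's implant

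*SAP*

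**What the plan says.** SAP 15.1 (Implanted Devices) takes three fields from the device log: device or lead type (`DIDVTYP`), status (`DTDVSTAT`) and model (`DIDVMDL`). Status has six values. Besides implanted and active they include "Deactivated but still implanted", "Explanted and discarded" and "Attempted implantation, then discarded".

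The derivations treat status differently:

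- **Leads (footnotes 30–33).** Each rule filters on status, for example "DIDVTYP = RA lead AND DTDVSTAT = Implanted and active".
- **Device model (footnote 29).** The rule selects on type only and then sets "device model SAR = DIDVMDL". Its type list opens with "DIDVTYP = Pacemaker (single/dual chamber) AND" and joins the remaining types by OR. SAP 16.1 repeats the analysis for pre-hospital discharge (PHD) and follow-up.
- **Device-type subgroup (SAP chapter 7, footnote 5).** The type must be non-missing, and then "subgroup device type SAR = helpvar device type".

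Protocol 7.5 asks for "Implant type and model, all other implanted devices". Protocol 11.9, repeated in SAP 5.6, uses device type to look for a connection between critical events and IPG, ICD, CRT or ICM.

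**The concern.** The device log is keyed by patient and device type (SAP 5.9), so one patient can have several generator rows. Both derived variables hold one value per patient. With no status condition and no rule for choosing among rows, an attempted, explanted or deactivated generator can supply the model, the subgroup or both.

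This matters because Protocol 11.2 expects unforeseen safety problems mainly from the software interaction between the programmer and the implanted device. Device type is the only subgroup factor planned. With few events expected (Protocol 5.3), tying one event to the wrong implant type could mislead that review.

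**Working it through.** The plan gives no figure on this point to reproduce, so the check applies the written rules to the possible log entries.

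**Step 1: is there a status filter elsewhere?** None was found.
- Footnote 28 restricts the accessory log, not the device log.
- SAP 15.3 excludes nothing.
- Footnote 2 seems meant to remove patients who received no implant. It tests `TIINC01 type` for a value that SAP 7.1 lists under `DSDRPPRO`. The values of `TIINC01 type` in SAP 8.2 do not include it, so the test removes nobody.

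**Step 2: which rows qualify for the device model?** Five generator types × six status values = 30 combinations.
- Footnote 29 read with OR throughout: 5 × 6 = 30 qualify, of which 30 − 5 = 25 are not implanted and active.
- Footnote 29 as written, AND binding before OR: one row cannot be both pacemaker and ICD, so only CRT-P, CRT-D and ICM remain. 3 × 6 = 18 qualify, of which 18 − 3 = 15 are non-active.
- Status condition added, AND kept: 3 × 1 = 3 qualify, with no pacemaker or single- or dual-chamber ICD among them.
- Status condition added and AND changed to OR: 5 × 1 = 5 qualify, one per generator type.

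These count rule outcomes. They are not patient frequencies.

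**Step 3: hypothetical patients.** The short-name list for the subgroup shows CRT and CRT-P; I take CRT to stand for CRT-D.

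| Log rows | Footnote 5 | Footnote 29 as written | Footnote 29 with OR | Corrected rule |
|---|---|---|---|---|
| Attempted CRT-D, active ICD | CRT-D or ICD | CRT-D | CRT-D or ICD | ICD |
| Explanted ICM, active IPG | ICM or IPG | ICM | ICM or IPG | IPG |
| Deactivated IPG, active CRT-D | IPG or CRT-D | CRT-D | IPG or CRT-D | CRT-D |
| Attempted IPG only | IPG | none | IPG | none |
| Attempted CRT-P, active CRT-P | CRT-P | two models | two models | one model |

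In the first two rows, footnote 29 as written returns only the non-active device. The fourth row shows that the status condition alone would leave a patient without a type. The fifth row affects the model only, and it would need two log rows with the same key.

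**Step 4: can such rows arise here?** Yes. Protocol 8.3.6 keeps a patient in the study after an unsuccessful implantation if another attempt is planned within 2 weeks. A patient with an earlier ICM is not barred from a de novo pacemaker. Protocol 7.5 asks for other implanted devices to be recorded.

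**The case against.** Five arguments can be made on the other side.

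- **The situation is uncommon.** Planned exchanges and upgrades are excluded (Protocol 8.3.3), ICM implantations are not studied (8.1.2), and the log is filled at baseline or at implantation (8.1.4.2). This stands. It lowers the frequency without closing the routes in step 4.
- **Most extra rows would not change the subgroup.** A same-type replacement leaves it unchanged, and a switch between CRT-P and CRT-D stays within the Protocol's single CRT group. This stands.
- **A deactivated generator still in the body belongs in a table of implanted devices.** This stands for a listing, given Protocol 7.5. It does not justify making that generator the patient's device model or subgroup, and it does not cover attempted or explanted devices.
- **Events are few and listed singly, so a wrong label would be noticed.** This stands in part. The SAP 10.2 listings give use case and programmer serial number but no implant type, so noticing it means going back to the device log.
- **A status line of footnote 29 may have been lost.** The neighbouring footnotes are laid out irregularly in the available text. This is possible but unproven, and it would not explain footnote 5.

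A reader might infer that a sizeable share of patients is misassigned, or that subgroup denominators are distorted. The documents do not support either. They give no count of patients with more than one generator row, and SAP chapters 10 and 11 specify no endpoint table by device type.

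**Conclusion.** The inconsistency is real and minor. As written, footnotes 5 and 29 can return a non-active generator as a patient's single value, while the lead rules in the same SAP prevent this. A wrong model needs a non-active generator row. A wrong subgroup needs that row to be of a different type from the active one, or no active generator at all.

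The effect is confined to the descriptive device table and the exploratory review of critical events by implant type. ADE and DD counts do not use these variables, and the sample-size reasoning does not depend on them. The size in patients cannot be stated from the documents. The conclusion assumes that the footnotes are programmed as written; a programmer might add the filter unprompted, but the SAP sets out to give detailed instructions.

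The AND in footnote 29 is a separate error in the same line. Taken literally it affects every pacemaker and every single- or dual-chamber ICD, so the status condition cannot repair the table on its own.

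**What to change.** 1. **Footnote 29:** replace the first AND by OR and, after the closing bracket, add `AND DTDVSTAT = Implanted and active`.
2. **Footnote 5:** add the same status condition.
3. **Non-active generators:** list attempted, explanted and deactivated generators separately, so that the Protocol 7.5 item on other implanted devices is still reported.
4. **No active generator:** a patient with only an attempted device stays in the implantation set under footnotes 2 and 3 if the programmer was used. Show the attempted type in its own category so that an event there still has a device type.
5. **Two active generators:** resolve by case review. The general-assessment variables listed in the SAP do not identify which generator was interrogated, so an automatic rule cannot be assumed.

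The cost is small: one condition in two footnotes, one operator, one listing and one extra category. The status field is already in the device log, so the filter needs no new data. Protocol 11.8 allows the SAP to be updated before database freeze or closure.

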**Renamic Neo and software**

Data file, identifier	Notes	Variable name	Variable label	Variable level	Nominal values
patient display id full & autom SVTYP					
accessory log details	No report	SVTYP	Visit type	nominal	o Implantation o Pre-hospital discharge o Follow-up

Data file, identifier	Notes	Variable name	Variable label	Variable level	Nominal values
patient display id full & SVTYP & helpvar model & DIPRGSNR					
accessory log details (see Analysis Set and Data Selection)	Selection DIPRGM DL = Renamic Neo; no report	DIPRGSNR	Programmer serial number	text	...
		DISFTVER	Programmer software version	nominal	NEO 2004.A ...

Note: In case of any reported problem, the serial number DIPRGSNR of the Renamic Neo, which was used for the specific investigation for a specific patient (or programmers in case more than one programmer were used), will be reported together with the patient id patient display id full.

Data file, identifier	Notes	Variable name	Variable label	Variable level	Nominal values
DIPRGSNR					
renamicneo SAR	descriptive	n imp per renamicneo SAR 	Number of implantations performed with specific Renamic Neo programmer	metric to be reported as nominal	1 2 ...

Data file, identifier	Notes	Variable name	Variable label	Variable Level	Nominal values
patient display id full					
data SAR	descriptive	n renamicneo imp SAR 	Number of Renamic Neo programmers used during implantation	metric to be reported as nominal	1 2 ...
		n renamicneo imp NEO2004A SAR 	Number of Renamic Neo programmers with software NEO 2004.A used during implantation	metric to be reported as nominal	1 2 ...

 Patient-specific data for lead RA model SAR = DIDVTYP = RA lead AND DTDVSTAT = Implanted and active DIDVMDL

 Patient-specific data for lead RV model SAR = DIDVTYP = RV lead AND DTDVSTAT = Implanted and active DIDVMDL

 Patient-specific data for lead LV model SAR = DIDVTYP = LV lead AND DTDVSTAT = Implanted and active DIDVMDL

 Patient-specific data for lead VCS model SAR = DIDVTYP = VCS lead AND DTDVSTAT = Implanted and active DIDVMDL

 Count different patient display id full per DIPRGSNR from accessory log details with SVTYP = Implantation

 Count different DIPRGSNR per patient display id full for SVTYP = Implantation

 Count different DIPRGSNR with DISFTVER = "NEO 2004.A" per patient display id full for SVTYP = Implantation

ECG cable

Data file, identifier patient display id full & SVTYP & helpvar model & DIPRGSNR	Notes	Variable name	Variable label	Variable level	Nominal values
accessory log details (see Analysis Set and Data Selection)	no report	DIECBMDL	ECG cable model	nominal	o PK-222-L ECG cable o PK-222 EU / 2.8 m ECG cable
		QSECBAS	Usage of ECG cable	nominal	o used successfully o used, but not successfully
		QSECBPRB	Did you notice any problems related to ECG cable	nominal	o Yes, with Adverse Event o Yes, without Adverse Event o No problem detected

Data file, identifier patient display id full & SVTYP & helpvar model & DIPRGSNR	Notes	Variable name	Variable label	Variable level	Nominal values
accessory log details (see Analysis Set and Data Selection)	case listing for QSECBAS = used, but not successfully OR QSECBPRB = Yes, with Adverse Event OR QSECBPRB = Yes, without Adverse Event including programmer serial number DIPRGSNR (see note before)	COECBAS	NEW: ECG cable at investigation: Please specify reason for unsuccessful use	text	...

Data file, identifier patient display id full	Notes	Variable name	Variable label	Variable Level	Nominal values
data SAR	descriptive	n ecgcable PK imp SAR 	Number of PK ECG cables used during implantation	metric to be reported as nominal	o 1 o 2 ...
		n ecgcable PK222L imp SAR 	Number of PK-222-L ECG cables used during implantation	metric to be reported as nominal	o 1 o 2 o ...
		n ecgcable PK222EU imp SAR 	Number of PK-222-EU ECG cables used during implantation	metric to be reported as nominal	o 1 o 2 ...
		n ecgcable nosuccess imp SAR 	Number of ECG cables not successfully used during implantation	metric to be reported as nominal	o 1 o 2 ...
		n ecgcable problem imp SAR 	Number of ECG cables with any problem used during implantation	metric to be reported as nominal	o 1 o 2 ...

 Count DIECBMDL = "PK-222-L ECG cable" OR "PK-222 EU / 2.8 m ECG cable" per patient display id full

 Count DIECBMDL = "PK-222-L ECG cable" per patient display id full

 Count DIECBMDL = "PK-222 EU / 2.8 m ECG cable" per patient display id full

 Count QSECBAS = "used, but not successfully" per patient display id full

 Count QSECBPRB = "Yes, with Adverse Event" OR "Yes, without Adverse Event" per patient display id full

Electrode clip

Data file, identifier patient display id full & SVTYP & helpvar model & DIPRGSNR	Notes	Variable name	Variable label	Variable level	Nominal values
accessory log details (see Analysis Set and Data Selection)	no report	DIELDCMD	Electrode clip model	nominal	o PK Electrode Clip
		QSELDCAS	Usage of electrode clip	nominal	o used successfully o used, but not successfully
		QSEDCPR	Did you notice any problems related to electrode clip	nominal	o Yes, with Adverse Event o Yes, without Adverse Event o No problem detected

Data file, identifier patient display id full & SVTYP & helpvar model & DIPRGSNR	Notes	Variable name	Variable label	Variable level	Nominal values
accessory log details (see Analysis Set and Data Selection)	case listing for QSELDCAS = used, but not successfully OR QSEDCPR = Yes, with Adverse Event OR QSEDCPR = Yes, without Adverse Event including programmer serial number DIPRGSNR (see note before)	COELDCAS	NEW: Electrode clip: Please specify reason for unsuccessful use	text	...

Data file, identifier patient display id full	Notes	Variable name	Variable label	Variable Level	Nominal values
data SAR	descriptive	n elclip pk imp SAR 	Number of PK electrode clips used during implantation	metric to be reported as nominal	o 1 o 2 ...
		n elclip pk nosuccess imp SAR 	Number of PK electrode clips not successfully used during implantation	metric to be reported as nominal	o 1 o 2 ...
		n elclip pk problem imp SAR 	Number of used PK electrode clips with any problem during implantation	metric to be reported as nominal	o 1 o 2 ...

 Count DIELDCMD = "PK Electrode Clip" per patient display id full

 Count QSELDCAS = "used, but not successfully" per patient display id full

 Count QSEDCPR = "Yes, with Adverse Event" OR "Yes, without Adverse Event" per patient display id full

Patient cable

Data file, identifier patient display id full & SVTYP & helpvar model & DIPRGSNR	Notes	Variable name	Variable label	Variable level	Nominal values
accessory log details (see Analysis Set and Data Selection)	no report	DIPCBDL	Patient cable model	nominal	
 
o Patient cable PK-141
 
o Patient cable PK-67-S
 
o Patient cable PK-67-L
 
o Patient cable PK-155
 

		QSPCBAS	Usage of patient cable	nominal	
 
o used successfully
 
o used, but not successfully
 

		QSPCBPRB	Did you notice any problems related to patient cable	nominal	
 
o Yes, with Adverse Event
 
o Yes, without Adverse Event
 
o No problem detected
 

Data file, identifier patient display id full & SVTYP & helpvar model & DIPRGSNR	Notes	Variable name	Variable label	Variable level	Nominal values
accessory log details (see Analysis Set and Data Selection)	case listing for QSPCBAS = used, but not successfully OR QSPCBPRB = Yes, with Adverse Event OR QSPCBPRB = Yes, without Adverse Event including programmer serial number DIPRGSNR (see note before)	COPCBAS	NEW: Patent cable: Please specify reason for unsuccessful use	text	...

Data file, identifier patient display id full	Notes	Variable name	Variable label	Variable Level	Nominal values
data SAR	descriptive	n patcable PK imp SAR 	Number of patient cables PK used during implantation	metric to be reported as nominal	o 1 o 2 ...
		n patcable PK141 imp SAR 	Number of patient cables PK-141 used during implantation	metric to be reported as nominal	o 1 o 2 o ...
		n patcable PK67S imp SAR 	Number of patient cables PK-67-S used during implantation	metric to be reported as nominal	o 1 o 2 ...
		n patcable PK67L imp SAR 	Number of patient cables PK-67-L used during implantation	metric to be reported as nominal	o 1 o 2 ...
		n patcable PK155 imp SAR 	Number of patient cables PK-155 used during implantation	metric to be reported as nominal	o 1 o 2 ...
		n patcable nosuccess imp SAR 	Number of patient cables not successfully used during implantation	metric to be reported as nominal	o 1 o 2 ...
		n patcable problem imp SAR 	Number of used patient cables with any problem during implantation	metric to be reported as nominal	o 1 o 2 ...

 Count DIPCBMDL = "Patient cable PK-141" OR "67-S" OR "67-L" OR "155" per patient display id full

 Count DIPCBMDL = "Patient cable PK-141" per patient display id full

 Count DIPCBMDL = "Patient cable PK-67-S" per patient display id full

 Count DIPCBMDL = "Patient cable PK-67-L" per patient display id full

 Count DIPCBMDL = "Patient cable PK-155" per patient display id full

 Count QSPCBAS = "used, but not successfully" per patient display id full

 Count QSPCBPRB = "Yes, with Adverse Event" OR "Yes, without Adverse Event" per patient display id full

Patient adapter

Data file, identifier patient display id full & SVTYP & helpvar model & DIPRGSNR	Notes	Variable name	Variable label	Variable level	Nominal values
accessory log details (see Analysis Set and Data Selection)	no report	DIPADMDL	Patient adapter model	nominal	o Patient adapter PA-1-B o Patient adapter PA-1-C o Patient adapter PA-2
		QSPADAS	Usage of patient adapter	nominal	o used successfully o used, but not successfully
		QSPADPRB	Did you notice any problems related to patient adapter	nominal	o Yes, with Adverse Event o Yes, without Adverse Event o No problem detected

Data file, identifier patient display id full & SVTYP & helpvar model & DIPRGSNR	Notes	Variable name	Variable label	Variable level	Nominal values
accessory log details (see Analysis Set and Data Selection)	case listing for QSPADAS = used, but not successfully OR QSPADPRB = Yes, with Adverse Event OR QSPADPRB = Yes, without Adverse Event including programmer serial number DIPRGSNR (see note before)	COPADAS	NEW: Patent adapter: Please specify reason for unsuccessful use	text	...

Data file, identifier patient display id full	Notes	Variable name	Variable label	Variable Level	Nominal values
data SAR	descriptive	n patadapt PA imp SAR 	Number of patient adapters PA used during implantation	metric to be reported as nominal	o 1 o 2 ...
		n patadapt PA1B imp SAR 	Number of patient adapters PA1B used during implantation	metric to be reported as nominal	o 1 o 2 o...
		n patadapt PA1C imp SAR 	Number of patient adapters PA1C used during implantation	metric to be reported as nominal	o 1 o 2 ...
		n patadapt PA2 imp SAR 	Number of patient adapters PA2 used during implantation	metric to be reported as nominal	o 1 o 2 ...
		n patadapt nosuccess imp SAR 	Number patient adapters not successfully used during implantation	metric to be reported as nominal	o 1 o 2 ...
		n patadapt problem imp SAR 	Number of used patient adapter with any problem during implantation	metric to be reported as nominal	o 1 o 2 ...

 Count DIPADMDL = "Patient adapter PA-1-B" OR "PA-1-C" OR "PA-2" per patient display id full

 Count DIPADMDL = "Patient adapter PA-1-B" per patient display id full

 Count DIPADMDL = "Patient adapter PA-1-C" per patient display id full

 Count DIPADMDL = "Patient adapter PA-2" per patient display id full

 Count QSPADAS = "used, but not successfully" per patient display id full

 Count QSPADPRB = "Yes, with Adverse Event" OR "Yes, without Adverse Event" per patient display id full

Accessory bag

Data file, identifier patient display id full & SVTYP & helpvar model & DIPRGSNR	Notes	Variable name	Variable label	Variable level	Nominal values
accessory log details (see Analysis Set and Data Selection)	no report	QSACCBAS	Usage of accessory bag	nominal	o used successfully o used, but not successfully
		QSACCBPR	Did you notice any problems related to patient adapter	nominal	o Yes, with Adverse Event o Yes, without Adverse Event o No problem detected

Data file, identifier patient display id full & SVTYP & helpvar model & DIPRGSNR	Notes	Variable name	Variable label	Variable level	Nominal values
accessory log details (see Analysis Set and Data Selection)	case listing for QSACCBAS = used, but not successfully OR QSACCBPR = Yes, with Adverse Event OR QSACCBPR = Yes, without Adverse Event including programmer serial number DIPRGSNR (see note before)	COACCBAS	NEW: Accessory bag: Please specify reason for unsuccessful use	text	...

Data file, identifier patient display id full	Notes	Variable name	Variable label	Variable Level	Nominal values
data SAR	descriptive	n abag imp SAR 	Number of accessory bags used during implantation	metric to be reported as nominal	o 1 o 2 ...
		n abag nosuccess imp SAR 	Number of accessory bags not successfully used during implantation	metric to be reported as nominal	o 1 o 2 o ...
		n abag problem imp SAR 	Number of used accessory bag with any problem during implantation	metric to be reported as nominal	o 1 o 2 ...

 Count non-missing QSACCBAS per patient display id full from the above selection of accessory log details

 Count QSACCBPR = "used, but not successfully" per patient display id full from the above selection of accessory log details

 Count QSACCBPR = "Yes, with Adverse Event" OR "Yes, without Adverse Event" per patient display id full from the above selection of accessory log details

